Auricular Vagus Nerve Stimulation (aVNS) regulates central nervous system function and influences neural activity in the brain by stimulating the vagus nerve branch in the concha region, showing broad application prospects in the field of neuropsychiatric diseases in recent years [1]. The intervention methods for aVNS include electrical stimulation of the transcutaneous auricular vagus nerve and stimulation of the auricular acupoint vagus nerve. Auricular acupuncture, a microsystem therapy, is theoretically based on the reflective correspondence between specific auricular points and system-level functional areas. This method simulates the effects of conventional invasive vagus nerve stimulation by applying needles to the auricle, thereby providing new avenues for treating conditions such as epilepsy, depression, pain, and cardiac diseases. The existing literature shows that auricular acupuncture vagus nerve stimulation has been investigated in several diseases, demonstrating its efficacy for depression [2], migraine [3, 4], and other conditions. Clinically, auricular acupuncture has proven to be significantly effective for anxiety and pain. Similar to body acupuncture, auricular acupuncture reduces preoperative anxiety, indicating comparable efficacy to traditional body acupuncture in anxiety relief [5]. Furthermore, auricular acupuncture has an analgesic effect on acute pain (such as sore throat), reducing pain scores and the need for analgesic medications [6]. In temporomandibular joint pain, auricular acupuncture, as an adjuvant therapy, can synergistically enhance the effects of conventional treatment, further supporting its ability to modulate pain pathways [7]. As anxiety and pain are common triggers of sleep disorders, auricular acupuncture may indirectly improve sleep quality by alleviating anxiety. These improvements may be related to the upregulation of plasma Brain-Derived Neurotrophic Factor (BDNF) levels [8]. Although these findings confirm the clinical efficacy of aVNS, the central nervous system mechanism of action has not been fully elucidated.

Studies suggest that aVNS may affect brain function through multiple pathways, including the modulation of neurotransmitter release, neurotrophic factor expression, and neuroinflammatory responses [8]. In particular, BDNF, as an important neurotrophic factor, is not only related to the efficacy of aVNS but may also participate in neuroplastic processes, affecting brain network functional reorganization. However, current research on how aVNS

modulates the functional connectivity of specific brain networks—especially neural networks closely related to cognition and emotion regulation, such as those involving the insula and medial prefrontal cortex—remains insufficient.

Resting-state functional magnetic resonance imaging (rs-fMRI) provides a key tool for investigating the modulation effects of Vagus Nerve Stimulation (VNS) on brain functional connectivity (FC) by measuring the blood-oxygen-level-dependent (BOLD) signal arising from spontaneous neural activity in the absence of tasks. Functional connectivity (FC), which refers to temporal correlations in spontaneous neural activity between distinct brain regions, is known to be aberrant in various neurological disorders [8-9]. Specific studies have demonstrated that aVNS can significantly modulate FC in multiple brain networks. Studies have indicated that aVNS attenuates negative FC between the insula and the medial prefrontal cortex (mPFC), a mechanism that may enhance the balance between interoceptive awareness and cognitive experience [1]. In patients with primary insomnia, rs-fMRI analyses revealed that taVNS reduced FC between the mPFC and dorsal anterior cingulate cortex (dACC, part of the salience network), as well as between the mPFC and occipital cortex. This reduction in FC was positively correlated with improvements in the Pittsburgh Sleep Quality Index (PSQI) scores, suggesting that taVNS may improve sleep by modulating interactions between the default mode network (DMN), salience network, and the visual cortex [8]. Furthermore, in migraine research, repeated taVNS treatment modulated resting-state FC (rsFC) between brainstem areas (e.g., NTS, RN), the limbic system (bilateral hippocampus), pain-processing regions (bilateral postcentral gyri, thalamus, and mPFC), and basal ganglia (putamen/caudate). Notably, changes in rsFC between the RN and putamen were significantly correlated with a reduction in monthly migraine days, underscoring the role of taVNS in pain modulation pathways [9]. Another study on primary insomnia found that taVNS reduced FC between the basal forebrain (BF) and the visual cortex (e.g., middle occipital gyrus, fusiform gyrus), sensorimotor cortex (supplementary motor area), and mPFC. Weakening of the connection between the basal forebrain and middle occipital gyrus was associated with improvements in the Insomnia Severity Index (ISI). More importantly, baseline FC within the basal-forebrain–visual circuit predicts therapeutic response to taVNS, supporting its potential

as a biomarker for personalized treatment [10]. Recent research has shown that transcranial auricular vagus nerve stimulation (taVNS) effectively reduces negative functional connectivity between the insula and the medial prefrontal cortex (MPFC)[1]. This modulation of neural circuitry is linked to improvements in both proprioceptive awareness and emotional cognition, offering key insights into the therapeutic mechanisms of taVNS.

This study systematically investigates whether auricular acupuncture elicits neuromodulatory effects comparable to taVNS on functional connectivity between the insula and the medial prefrontal cortex (mPFC) in healthy subjects using resting-state functional magnetic resonance imaging (rs-fMRI). By characterizing the baseline neurophysiological effects of auricular acupuncture, the work clarifies its core regulatory mechanisms in cognition and mood. These findings establish key theoretical and evaluative frameworks for subsequent clinical translation in insomnia, depression, and related disorders.

二、Study Objectives

Primary Objective: This study investigates whether auricular acupuncture therapy can modulate the functional connectivity between the insula and medial prefrontal cortex (MPFC) via resting-state functional magnetic resonance imaging (rs-fMRI), similar to transcranial vagus nerve stimulation (taVNS), and analyzes its association with improvements in proprioceptive function.

Mechanistic Objective: To investigate how aVNS influences the integration of interoceptive processing (bodily signal processing) and cognitive function (cerebral cognitive processing) by examining its regulatory impact on this specific neural circuit.

三、Study Design

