3.5 Randomization and Blinding

The enrolled 32 subjects were randomly assigned in a 1:1 ratio to two groups: the real auricular acupuncture vagus nerve stimulation group (AA) and the sham auricular acupuncture control group (SA).

This study employed a double-blind design, meaning that neither the subjects in each group nor the acupuncturist knew whether they belonged to the AA group or the SA group.

The sham stimulation group used press needles without tips at the same acupoints, preventing the subjects from distinguishing whether they were receiving real or sham stimulation, thereby reducing expectancy effects. Randomization and allocation concealment were performed by an independent statistician, ensuring that neither the study participants nor the researchers could influence the assignment. The success of participant blinding was assessed using the Bang Blinding Index (BBI); blinding was considered successful when the BBI value was between -0.2 and 0.2.

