3.6 Interventions

3.6.1 Auricular Press Needle Acupuncture

Auricular Points: Heart, Kidney, Shenmen, Subcortex

① Before the application, the participants rested for 5 min, followed by baseline fMRI examination (including T1-weighted and T2-weighted images).

② After the examination, auricular press needles were inserted. The physician's hands and local acupoint areas were routinely disinfected. The experimental group used Dingshi brand disposable sterile press needles (with release paper, Medical Device Registration No.: Su Xie Zhu Zhun 20212200040, specification 0.20×1.3 mm). Disposable, sterile press needles without tips were used in the control group. The needle body was inserted at the aforementioned points, the release paper was removed, and the adhesive tape was gently pressed to ensure tight adhesion. Both ears were treated at each time-point.

③ After application, each acupoint was pressed 20 times. Pressing all eight points twice took approximately 2 min to complete. Rest for 10 min. A second pressing session was performed for 2 min. Rest for 10 min. A third pressing session was performed for 2 min, and the press needles were removed. (Total duration: approximately 26 min).

④ Immediately an fMRI examination (T2-weighted images only) was performed to observe changes in brain regions.

The intervention involved applying auricular press needles (a type of intradermal embedding needle) to specific acupoints.

[figure not shown]

Figure 1. Localization of selected auricular points.

Table 1. Common names, locations, and indications of auricular points.

Common Name	Acupuncture Point	Anatomical Location	Indications Based on TCM and Scientific Research	Mental Health and Depression Indications
Shenmen	TF4	The upper portion of the apex of the triangular fossa is closer to the upper branch of the antihelix.	Analgesic and anti inflammatory action is the most critical anesthesia point on the ear.	Sedative point. Calms the mind.
Heart	CO15	In the center of the cavum conchae	Used for cardiac complaints such as angina, cardiac rhythm disorders	Indicated for anxiety, depression, distress, mental agitation, and insomnia.
Kidney	CO10	In the cymba conchae, in a groove below the start of the inferior crus.	Used for issues in the urinary and genital systems. Assists with tinnitus, auditory conditions, and sleep disorders.	Indicated for fear, insecurity, and lack of willpower.

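### The aim promises effects comparable to taVNS, but a two-arm comparison with tipless needles at the same points cannot show that, and a null result would not rule out an effect of auricular stimulation

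*Combined protocol and SAP*

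**What the plan says.** The last paragraph before section 二 asks whether auricular acupuncture "elicits neuromodulatory effects comparable to taVNS on functional connectivity between the insula and the medial prefrontal cortex (mPFC". The primary objective in section 二 asks whether it can modulate the same connection in a way similar to taVNS. The mechanistic objective is "To investigate how aVNS influences the integration of interoceptive processing" and cognitive function.

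On design, section 3.5 states: "The enrolled 32 subjects were randomly assigned in a 1:1 ratio to two groups", AA and SA. On the control it states: "The sham stimulation group used press needles without tips at the same acupoints". Section 3.6.1, step 2, confirms this: "Disposable, sterile press needles without tips were used in the control group". Step 3 begins "After application, each acupoint was pressed 20 times" and describes three pressing sessions. It does not name an arm.

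The background describes aVNS as "stimulating the vagus nerve branch in the concha region" and adds: "The intervention methods for aVNS include electrical stimulation of the transcutaneous auricular vagus nerve and stimulation of the auricular acupoint vagus nerve".

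The primary outcome (3.7) is the T1–T0 change in insula–mPFC connectivity strength. Section 3.8.2 names the independent-samples t-test, the Mann–Whitney test and the chi-square test, with significance at P < 0.05.

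**The concern.** The aim and the contrast answer different questions. A test of AA against SA asks whether the two arms differ. A statement that AA is comparable to taVNS needs something from taVNS to compare with, and a rule for how close is close enough. The plan has neither.

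The choice of sham adds a second limit. SA receives a device at the same points, and by the background's own description stimulating auricular points is one way of delivering aVNS. Whatever contact at those points does to the circuit, it does in both arms.

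Two misreadings are therefore left open. A positive AA–SA result could be reported as confirming the taVNS comparison, which was never made. A null result could be reported as showing that auricular stimulation does not affect the circuit, even if both arms moved together.

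**Working it through.** **1. What comparability would need, and what the plan has.**

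| Needed | In the plan |
|---|---|
| A taVNS arm or a taVNS reference value | Neither (3.5; background) |
| An equivalence or non-inferiority margin | None |
| A test against that margin | None; difference tests only (3.8.2) |
| At minimum, a prespecified direction | None (3.7) |

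On the last row, the background reports that taVNS makes a negative insula–mPFC connection less negative. Section 3.7 does not adopt this as a criterion. It interprets an increase as better integration and a decrease as relief of excess connectivity. It also speaks of connectivity strength without saying whether the sign is kept. A negative connection that becomes less negative rises in signed value and falls in absolute strength, so the direction must be stated on the signed scale.

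**2. What AA–SA contains.** Assume that effects add and blinding holds, so that time, repeat scanning and expectation are equal in both arms.

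- AA change = time and expectation + contact + pressing + needle tip.
- SA change, if pressed identically = time and expectation + contact + pressing. Then AA–SA = needle tip.
- SA change, if not pressed = time and expectation + contact. Then AA–SA = needle tip + pressing.

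In neither case is there a taVNS term, so no sample size turns this contrast into a comparison with taVNS. In both cases the contact effect cancels.

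**3. Where the shared points lie (Table 1).** Heart is in the cavum conchae and Kidney in the cymba conchae, so both are in the region the background gives as the vagal target. Shenmen (triangular fossa) and Subcortex (antitragus) are outside it. All four are used in both arms.

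**4. Precision that follows from 16 per arm,** in SD units of the T1–T0 change.

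- AA–SA: 95% half-width = t(0.975, 30 df) × √(2/16) = 2.042 × 0.354 = 0.72 SD.
- One arm's mean change: t(0.975, 15 df) / √16 = 2.131 / 4 = 0.53 SD.

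**5. Illustrations only.** Section 3.3 cites a minimum of 12 subjects at a threshold of 0.05 but gives no effect size or SD for insula–mPFC connectivity. That figure cannot be reproduced, and nothing here depends on it.

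*Shared effect.* With 16 per arm and two-sided 0.05 (assumed, since the sides are not stated), the effect detectable with 80% power is 1.02 SD (t-test). Suppose this were the total AA effect against an inert control, and a share f of it also occurred in SA. Then AA–SA = 1.02 × (1 − f), with power from the noncentral t (30 df, noncentrality = difference × √8):

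| f (assumed) | AA–SA | Power |
|---|---|---|
| 0% | 1.02 SD | 80% |
| 20% | 0.82 SD | 61% |
| 30% | 0.72 SD | 50% |
| 50% | 0.51 SD | 29% |

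*Equivalence.* In a hypothetical AA against taVNS trial with 16 per arm and a true difference of zero, two one-sided 5% tests would conclude equivalence within 0.5 SD about 0.8% of the time, and within 0.8 SD about 43% of the time (simulation).

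**The case against.** A tipless needle at the same points is a legitimate control. The background also describes the method as applying needles to the auricle, and 3.6.1 calls the device an intradermal needle. On that reading the needle is the intervention, and the sham isolates its specific effect while holding contact and expectation constant. This stands: the sham is valid for that question, and the primary objective does concern auricular acupuncture.

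The taVNS wording can also be read as a loose analogy with a published effect, since no equivalence test is planned. That is a fair reading of 'similar', but less so of the aim's stronger wording. Even the loose reading needs a direction, which 3.7 does not fix.

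Section 3.7 already plans pre–post comparison in participants receiving auricular acupuncture, so a shift in AA would be seen. This partly stands. What is not specified is the SA change alongside it with an interval for each.

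A reader might go further and infer that AA–SA measures only the needle tip. The documents do not support that without conditions. They do not say that SA needles were pressed: step 3 is silent on the arm, and the masking aim makes equal pressing likely but not stated. The reading also needs additivity and intact blinding. Nor do the documents plan a conclusion in the words 'aVNS modulates'; the nearest text is the mechanistic objective's question about how aVNS influences processing. The two misreadings described above are risks that the wording leaves open, not conclusions the plan commits to.

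**Conclusion.** The point holds as a mismatch between the stated aim and the randomised contrast. Comparability with taVNS cannot be concluded from AA–SA. This rests on the design alone: two arms, no taVNS reference, no margin, difference tests. Directional agreement with the published taVNS effect is not tested as the plan stands.

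The second limb is conditional. Under additivity and intact blinding, and if SA was pressed identically, AA–SA estimates the added effect of the needle tip. If SA was not pressed, it mixes tip and pressing. Either way, a null result does not show that auricular stimulation has no effect, and the interval of about ±0.72 SD shows how wide a range a null could leave open.

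The power and equivalence figures in step 5 should not be read as findings of low power. The shared fraction, the total effect and the margins are assumptions with no source in the documents.

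The randomised comparison itself remains sound for the narrower question.

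**What to change.** 1. In the aim and section 二, replace the wording on comparability or similarity with taVNS by: changes insula–mPFC zFC more than tipless needles at the same points. Allow at most a statement that the change is in the same direction as the published taVNS effect, with that direction (less negative connectivity, on the signed scale) prespecified in 3.7.
2. State in advance that a null AA–SA result does not show absence of an auricular-stimulation effect.
3. Report the T1–T0 mean with its 95% confidence interval for each arm, descriptively, next to the between-arm difference, so that a shift common to both arms is visible. A within-arm change also carries time, repeat scanning and expectation, so it should not be tested as an effect of treatment.
4. Reconcile 3.5 and 3.6.1 by stating whether the pressing sessions were applied identically in SA.

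The cost is a few sentences and one table, with no new participants, scans or procedures. The downside is a narrower headline claim.

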3.1 Design Type

This was a parallel-group, randomized, sham-controlled clinical trial.

The study was conducted in accordance with the Consolidated Standards of Reporting Trials (CONSORT) guidelines and the Standards for Reporting Interventions guidelines. All participants provided written informed consent prior to participation and received incentives or compensation for participating in the study.

3.2 Study Population and Recruitment

Healthy adults were recruited from Taizhou People's Hospital through hospital outpatient

clinics and promotional posters on the hospital's official WeChat accounts. The study adhered to the principle of voluntary participation, and all subjects were required to sign an informed consent form before enrollment. All participants were assessed and screened by a physician.

3.3 Sample Size

The sample size estimation for functional MRI (fMRI) studies was based on Desmond's research findings. When analyzing fMRI data using a liberal threshold of 0.05, at least 12 subjects are required to achieve 80% or higher activation intensity at the single-voxel level [11]. This study randomly recruited 32 subjects, with 16 subjects per group, to systematically analyze changes in brain function before and after auricular acupuncture intervention, combined with its efficacy.

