3.7 Observational Indicators

Resting-state functional magnetic resonance imaging was used to conduct pre- and post-intervention comparative analyses in participants receiving auricular acupuncture.

Data collection is divided into two stages:

Baseline: Collection of demographic data, baseline fMRI scan, and clinical assessment (T0).

post-intervention:fMRI scan and clinical assessment immediately after the intervention (T1).

Primary Outcome Measure

Functional connectivity strength between the insula and the medial prefrontal cortex (MPFC)(T1-T0)

This connectivity strength serves as a proxy for the efficiency of information exchange between the “interoceptive hub” and “the self-referential/emotion-regulatory hub”. An increase following auricular acupuncture may reflect enhanced psychosomatic integration and top-down emotional regulation, suggesting a functional optimization of this circuit. Conversely, a decrease could indicate a disruption of pathological hyper-connectivity related to emotional constraint or an upregulation of control—mechanisms consistent with the observed alleviation of emotional symptoms

Secondary Outcome Measures

①Local brain activity indicators:regional homogeneity (ReHo), amplitude of low-frequency fluctuation (ALFF), fractional ALFF (fALFF)(T1-T0);

ReHo captures the temporal synchrony of neural activity within local brain regions. Following auricular acupuncture, increased ReHo in regions such as the insula and prefrontal cortex may reflect improved neural coordination and functional integration. Conversely, decreased ReHo in specific areas could indicate a modulatory effect on abnormally elevated local synchrony.

ALFF reflects the intensity of spontaneous neural activity in the brain. An increase in ALFF within emotion- and cognition-related regions following auricular acupuncture may indicate an elevation in baseline neural activity or metabolic activity in these areas. Conversely, a decrease in ALFF in regions such as the limbic system could reflect an

inhibitory modulatory effect of the intervention on hyperactivity, potentially contributing to emotional stabilization.

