3.8 Functional Image Processing and Statistical Analysis

3.8.1 Resting-state fMRI Data Processing

All functional imaging data were processed and analyzed using MATLAB R2022b (MathWorks) with the SPM12 toolkit, RESTplus v1.25, and DPABI v7.0 software packages. The preprocessing steps included: ①data format conversion; ②removal of the first 10 time points to eliminate unstable initial signals; ③head motion realignment and slice-timing correction. Individuals with head movements exceeding 2 mm or 2 degrees were removed; ④spatial normalization to the Montreal Neurological Institute template using the DARTEL registration algorithm, followed by resampling to an isotropic voxel size of $3\text{ mm} \times 3\text{ mm} \times 3\text{ mm}$; ⑤spatial smoothing using a 6-mm Gaussian kernel; ⑥linear detrending; ⑦regression of nuisance covariates, including 24-head motion parameters, white-matter signal, and cerebrospinal fluid signal; ⑧application of a 0.01 to 0.08 Hz bandpass filter.

Mean Regional Homogeneity (mReHo): ReHo maps were generated by calculating

Kendall's coefficient of concordance (KCC) using RESTplus V1.25 software. To minimize individual differences, the ReHo value of each voxel was normalized by dividing it by the global mean ReHo value of the entire brain, resulting in mReHo.

Mean Amplitude of Low-Frequency Fluctuation (mALFF) and its derived metric, mean fractional ALFF (mfALFF): The time series of each voxel was transformed into the frequency domain using a Fast Fourier Transform (FFT) to obtain the power spectrum. ALFF was calculated as the square root of the power spectrum. fALFF was defined as the ratio of the ALFF value in the low-frequency range (0.01–0.08 Hz) to the ALFF value across the entire frequency range (0–0.25 Hz). To minimize individual variability, the fALFF value of each voxel was normalized by dividing it by the global mean fALFF value of the whole brain, resulting in the mfALFF.

Functional images were transformed into a mirrored space after preprocessing. The mean BOLD time series for each voxel was extracted. Pearson's correlation coefficients were computed for mirrored voxels from the bilateral hemispheres to produce VMHC maps. The Fisher-z transform was used to enable subsequent group-level comparisons.

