Z-score normalized Functional Connectivity (zFC) values: Brain regions exhibiting significant between-group differences in functional metrics were defined as regions of interest (ROIs). Functional connectivity between each ROI and the entire brain was computed using the RESTplus software. The resulting correlation coefficients were subsequently standardized using Fisher's r-to-z transformation to obtain zFC values.

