3.8.2 Clinical Data

Datasets: Intent-to-Treat (ITT) and Per-Protocol (PP) analyses were used.

Normally distributed continuous data were described as mean \pm standard deviation, and inter-group comparisons for normally distributed variables used independent-samples t-tests. Non-normally distributed scale data will be described as medians and interquartile ranges, and the Mann–Whitney U non-parametric test will be used for statistical analysis. Categorical data were analyzed using the Chi-square test.

All statistical analyses were performed using SPSS or R software. Statistical significance was set at $P < 0.05$.

四、Ethics and Participant Protection

Before the study begins, the study protocol (including questionnaires and the informed consent form) will be submitted for review and approval to the Ethics Committee of Taizhou People's Hospital Affiliated to Nanjing Medical University (ethics number: LSKY 2025-175-01). Any amendments to the study protocol will be submitted to the Ethics Committee for approval and record-keeping. All participants will be fully informed about the study purpose, procedures, potential risks, and benefits, and will provide written informed consent.

五、References

- [2] de Oliveira Rodrigues DM, Menezes PR, Machado Ribeiro Silotto AE, et al. Efficacy and Safety of Auricular Acupuncture for Depression: A Randomized Clinical Trial [J]. *JAMA Netw Open.* 2023;6(11):e2345138.

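### The only seed-based connectivity pipeline (3.8.1) lets significant trial results choose the regions, so it need not deliver the insula-mPFC primary outcome; the sample-size basis in 3.3 is not linked to that outcome either

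*Combined protocol and SAP*

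**What the plan says.** All references are to the combined protocol and SAP.

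- **Primary outcome (3.7):** "Functional connectivity strength between the insula and the medial prefrontal cortex (MPFC)(T1-T0"). Two regions are named. No atlas, mask, coordinates or hemisphere is given.
- **Connectivity processing (3.8.1, zFC values):** "Brain regions exhibiting significant between-group differences in functional metrics were defined as regions of interest (ROIs"). Then: "Functional connectivity between each ROI and the entire brain was computed using the RESTplus software". The coefficients are Fisher-z transformed, and the description stops there.
- **Design (3.1, 3.5):** a parallel-group, sham-controlled trial. "The enrolled 32 subjects were randomly assigned in a 1:1 ratio to two groups".
- **Sample size (3.3):** the only support is a cited figure: "using a liberal threshold of 0.05, at least 12 subjects are required to achieve 80% or higher activation intensity at the single-voxel level". The section then gives 16 per group, with no step between the two numbers.
- **Losses (3.8.1, preprocessing):** "Individuals with head movements exceeding 2 mm or 2 degrees were removed". No expected rate is given.
- **Test and level (3.8.2, headed Clinical Data):** "inter-group comparisons for normally distributed variables used independent-samples t-tests", and "All statistical analyses were performed using SPSS or R software. Statistical significance was set at" P < 0.05. Sidedness is not stated, and no correction across voxels, metrics or regions is named anywhere.

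**The concern.** The primary outcome is a named connection, but the written method for obtaining connectivity does not start from it. It starts from whichever regions separate the arms on other imaging metrics. A connection reported as the main finding could therefore have been selected by the data it is tested on. A reader could not tell one planned comparison at 0.05 from the product of a search.

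The sample-size text adds to the uncertainty. It concerns one voxel, while the primary outcome is a change in connectivity between two regions, compared between two arms. What 32 participants can show depends on which connectivity analysis is primary, and the plan leaves that open.

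**Working it through.** **1. Does 3.8.1 produce the outcome in 3.7?** Follow the rule as written through the possible results of the first step:

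- Neither the insula nor the mPFC separates the arms: neither becomes a seed, and no insula-mPFC value is produced.
- Only other regions separate the arms: connectivity is computed for those, so the values obtained are not the primary outcome.
- The insula (or the mPFC) does separate the arms: its map covers the other region. But the seed is whatever part reached significance, on whichever side, and the target has no defined extent.
- Several regions qualify: there are several seeds, each mapped to the whole brain, and no rule says which value is primary.

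Only the third result, or the fourth if it includes one of the two regions, leads to the primary outcome. Even then the trial data set its definition. VMHC, also in 3.8.1, is a connectivity measure too, but it links mirrored voxels across hemispheres, is secondary, and does not measure insula-mPFC connectivity.

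**2. Can the figure in 3.3 be reproduced?** No. Effect size, SD and sidedness are missing, the 80% is not worded as a power, and the text does not say whether 12 is a total or per group. Solving backwards from 12 at alpha 0.05 and an assumed 80% power gives:

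- one-sample t: 0.89 SD (two-sided) or 0.77 SD (one-sided);
- two-sample t, 12 per arm, two-sided: 1.20 SD.

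The text does not choose between these, and none of them leads to 16.

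**3. What does 16 per arm give for one fixed connection?** Inputs from the documents: 16 per arm (3.3) and 0.05 (3.8.2). Assumed: two-sample t-test on the T1-T0 change, two-sided, 80% power, no losses. The SD is that of the change.

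- Power = P(T > t\* | df, δ), where T is noncentral t, df = 2n − 2, δ = d·√(n/2), and t\* is the two-sided critical value.
- n = 16: df = 30, t\* = 2.042, √8 = 2.828. Power is 0.800 at d = 1.024, where δ = 2.90. The normal approximation (1.960 + 0.842)·√(2/16) gives 0.99.
- Power at 0.8 SD is 59%; at 0.5 SD it is 28%.
- n = 14 (illustrative motion loss): 80% power at 1.10 SD.
- n = 16, two connections each at 0.025: 80% power at 1.14 SD.
- 95% CI half-width = t\*·√(2/n), in SD units. At n = 16: 2.042 × 0.3536 = 0.72. At n = 14: 2.056 × 0.3780 = 0.78.

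These figures apply to one connection chosen in advance (or two, where stated). They do not apply to a whole-brain search or to regions selected by significance.

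**The case against.** **The target is already named.** Section 3.7 and the primary objective specify insula-mPFC connectivity, and 3.8.1 never says that its data-selected regions supply the primary outcome. That paragraph may be meant as a follow-up to the ReHo, ALFF and VMHC maps. This is fair, and selection of the primary connection by the data is a possibility, not a declared plan. But no other route to a seed-based value is written, and naming two large regions does not define them.

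**The plan does not say that it tests the whole brain at an uncorrected 0.05.** A reader might infer this, together with a high false-positive rate. The documents do not support it: 3.8.1 says that connectivity was computed and writes no test for the maps, and the 0.05 level stands under Clinical Data. Estimates of false regions or voxelwise detectable effects would describe analyses that the plan does not state. What stands is that neither a test nor a correction is named.

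**The comparison could be within arm.** Section 3.7 speaks of pre- and post-intervention comparisons in those receiving auricular acupuncture, and 3.3 of changes before and after. On that reading, 16 participants give 80% power at about 0.75 SD (paired t, two-sided 0.05). However, randomisation against sham makes the between-arm comparison of the change the sensible primary test.

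**The trial is too small.** A reader might infer this from 3.3. The documents do not show it: 3.3 claims no power for the between-arm contrast that the design then misses, no target effect is given, and 16 per group may be 12 plus a margin, although the text does not say so. The wording about activation intensity may be a slip for power. That can be settled only against the cited reference, so it is not counted here as a defect.

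**Conclusion.** The point holds as a gap in the analysis specification, of minor severity. The firm part needs no assumptions: the seed rule in 3.8.1 and the primary outcome in 3.7 do not meet, and the region definitions, side, connectivity test and multiplicity correction are all absent. The sample-size part is weaker. Section 3.3 does not link its single-voxel figure to the primary outcome, but nothing shows that 32 is the wrong number.

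The size of what the design can show is about 1.02 SD of the change at 80% power, with a 95% CI half-width of about 0.72 SD. Both rest on a two-sample t-test, two-sided 0.05, all 32 participants evaluable and one connection fixed in advance; the first also rests on the choice of 80% power. The documents give no SD or expected effect, so these figures cannot be translated into Fisher-z units or judged for relevance.

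**What to change.** N, allocation and the named primary outcome stay as they are.

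1. **In 3.8.1**, define the insula and mPFC regions and the side for the primary outcome from a source independent of the trial data. If both sides are used, either average them into one value or split alpha. Name the AA-versus-SA test of the T1-T0 change as the primary analysis. Label the significance-based region search as secondary or exploratory, and name its multiple-comparison correction. If group results have already been seen, say that the choice was made afterwards.
2. **In 3.3**, state that the single-voxel figure is not a power claim for the between-arm contrast. Optionally add: *For one pre-specified insula-mPFC connection, assuming a two-sample t-test on the T1-T0 change, two-sided 0.05 and no losses, 16 per arm gives 80% power for a difference of about 1.02 SD of the change (about 1.10 SD at 14 per arm) and an expected 95% CI half-width of about 0.72 SD. This does not apply to whole-brain or data-selected analyses.* If recruitment is complete, label the sentence as added afterwards.

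The cost is some text and one constraint: a connection found only through the significance-based search is reported as secondary. No extra participants or scans are needed.
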